10.4 Subjective scales

TSS (−4...+4; anchors from very cold to very hot), CS (1...5; comfortable to extremely uncomfortable), VAS pain (0–100 mm; no pain to worst pain imaginable). Scripted instructions by the same assessor.

11. Sample Size

An a priori power analysis (G*Power 3.1.9.7) for a two-tailed independent-samples t-test ($\alpha = 0.05$, power = 0.80, anticipated effect size $d = 0.80$) indicated a required sample of 26 participants per group (total $n = 52$). In practice, 39 participants were enrolled and randomised (experimental $n = 20$; control $n = 19$). Of 40 individuals assessed, one was excluded at screening for a health condition. No participants discontinued the intervention or were lost to follow-up. With the achieved sample size, post-hoc power to detect $d = 0.80$ was approximately 0.68; accordingly, findings are interpreted as exploratory/hypothesis-generating.

12. Randomization and Allocation

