12.3. Blinding

Participants and interventionists were not blinded. Thermal image analysis was performed offline by an assessor not involved in data collection. Raw-data preprocessing/curation ([name]) and statistical analyses ([name]) were conducted by team members who did not take part in the experimental procedures and were blinded to group allocation.

13. Statistical Analysis Plan (SAP)

- **Descriptives:** values as mean \pm SD; Table 1 additionally reports min–max where shown.
- **Normality:** Shapiro–Wilk test.
- **Between-group comparisons at prespecified time points:** Student’s t test (normal) or Mann–Whitney U test (non-normal).
- **Within-group pre–post comparisons:** paired Student’s t test (normal) or Wilcoxon signed-rank test (non-normal).
- **Repeated measures:** two-way repeated-measures ANOVA for Tsk (group \times stage; and IRT vs RT within groups), with Bonferroni-adjusted post hoc tests. Effect size: partial η^2 for RM-ANOVA.
- **Significance:** $\alpha = 0.05$; tests two-sided.
- **Analysis set / missing data:** all randomised participants analysed; no imputation (no losses).

14. Data Management and Sharing

De-identified individual participant data (IPD) and the de-identified summary datasets underlying all tables and figures are openly available in Zenodo (DOI: 10.5281/zenodo.17255092) under a CC BY 4.0 license, with no access restrictions or data-use agreement required. The Zenodo record also includes Supplementary File S1 (exact questionnaire wording/anchors) and the full Research Protocol and prespecified Statistical Analysis Plan. De-identified IPD comprise participant-level values for prespecified outcomes and baseline characteristics; direct identifiers, dates, free-text fields, and rare categories were removed or aggregated to minimise re-identification risk. The dataset will be preserved for at least 5 years; enquiries may be directed to the corresponding author.

15. Ethics

Approved by the Bioethics Committee of the Poznań University of Medical Sciences (Resolution No. 360/11). Conducted in accordance with the Declaration of Helsinki. Minimal risk expected.

16. Monitoring and Harms

Adverse events (e.g., excessive pain, skin irritation) monitored throughout; any event recorded with timing, severity, relatedness, and action taken. No interim analyses; trial duration per session ~60–75 minutes.

17. Amendments and Deviations

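### A Shapiro–Wilk result decides whether means or ranks are compared, so the target can change between outcomes and stages; rejections clearly mislead about means only where an outcome is skewed and its spread differs between arms

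*Combined protocol and SAP*

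**What the plan says.** Section 13 lists a normality check, "Shapiro–Wilk test", and then gives the between-group rule: "Student’s t test (normal) or Mann–Whitney U test (non-normal". Within-group comparisons switch in the same way: "paired Student’s t test (normal) or Wilcoxon signed-rank test (non-normal". The SAP gives no threshold for the pretest. It does not say whether the pretest is applied per arm, pooled or to residuals, and it offers no unequal-variance t test. Descriptives are "values as mean \pm SD" whichever test is used.

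Skin temperature also gets a "two-way repeated-measures ANOVA for Tsk" by group and stage, with Bonferroni post hoc tests. The normality rule does not govern that analysis.

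Section 8.1 defines the primary endpoint as one value per person, the lowest IRT temperature over stages IV–X, compared between groups. Section 13 names no separate test for it. The sample size in Section 11 rests only on a "two-tailed independent-samples t-test", and the same section calls the findings exploratory.

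**The concern.** Student's t test compares means. Mann–Whitney concerns the probability that a value from one arm exceeds a value from the other. When a pretest on about 20 values per arm picks between them, the question answered can differ between outcomes, and between stages of one outcome, while the reader sees means and SDs throughout. The primary endpoint appears to fall under the same rule, although it was sized for a comparison of means.

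Several secondary outcomes could plausibly be non-normal. MDT filaments run from 0.008 to 300 g, VDT is read on a 0–8 scale, and TSS, CS and VAS are bounded. A thermoneutral arm could sit near the VAS floor while ice responses spread out. If an outcome is skewed and its spread differs between arms, Mann–Whitney can reject although the means are equal, and a table of means invites the reader to take that as a mean difference.

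**Working it through.** **Inputs.** From the documents: 20 ice and 19 control participants, two-sided alpha 0.05, d = 0.80, power 0.80 (Sections 11 and 13), and eight matched Tsk stages, I and IV–X (Section 8.2). Assumed, because the documents are silent: Shapiro–Wilk at 0.05 in each arm, t if both arms pass and Mann–Whitney otherwise; all distribution shapes; all spread ratios.

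**1. The plan's own figures.** Noncentrality is d × √(n1·n2/(n1+n2)).
- At 26 per arm: 0.80 × √13 = 2.88, power 0.807. At 25 per arm, power is 0.791. So 26 per arm is reproduced.
- At 20 and 19: 0.80 × √(380/39) = 2.50, power 0.682. The stated 0.68 is reproduced.

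**2. How often the test switches when all data are normal.**
- One comparison: 1 − 0.95² = 0.0975. Simulation gives 9.7–10.2%. The single primary comparison has this chance.
- At least one of eight Tsk stages, if independent: 1 − 0.9025⁸ = 0.56. Without baseline, seven stages: 1 − 0.9025⁷ = 0.51.
- With within-person correlation 0, 0.6 and 0.8, 1,500 simulated trials gave 54.8%, 52.5% and 49.5% for eight stages. Other runs at correlations of 0 to 0.8 gave 46–56%, and 34% at 0.95.

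**3. Rejection rate of the planned rule with equal true means.** 20,000 trials per cell, 20 against 19, wider spread in the ice arm. Simulation error near 5% is √(0.05 × 0.95/20,000) = 0.15 percentage points.

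| Shape in both arms | SD ratio 1 | 2 | 3 | 5 | Sent to Mann–Whitney | Welch, ratios 1–5 |
|---|---|---|---|---|---|---|
| Normal | 5.1% | 5.0% | 5.7% | 6.1% | about 10% | 4.8–5.2% |
| Heavy-tailed symmetric (t, 4 df) | 4.9% | 5.2% | 5.9% | 6.3% | about 42% | 4.6–4.8% |
| Moderate skew (gamma, shape 4) | 5.3% | 7.5% | 9.4% | 11.4% | 48–49% | 4.6–5.9% |
| Strong skew (exponential) | 4.8% | 18.0% | 24.4% | 28.8% | about 97% | 4.4–8.2% |

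With only the ice arm skewed and a normal control arm, ratios 2, 3 and 5 give 7.9%, 9.6% and 11.0% (gamma) and 16.1%, 22.4% and 28.0% (exponential).

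**4. A second skewed family: mean-centred lognormal, equal means.**
- Log-SD 0.2: 6.4–6.7% at ratios 2–3.
- Log-SD 0.3: 6.9–8.9%.
- Log-SD 0.4: 8.5–11.6%.
- Log-SD 0.6: 8.3% at 1.5:1, about 14% at 2:1 (Welch 6.2%), and 18.7–20.1% at 3:1 across separate runs (Welch 6.3–7.3%).

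**5. Power given up by fixing a mean comparison.** For an untransformed lognormal outcome with log-SD 0.6, equal spread and a 0.8 SD shift, Welch has about 72% power and the planned rule about 86% (70% and 87% in another run).

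**The case against.** Several points on the other side stand.

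- A reader might infer that unequal spread alone produces false findings. It does not: with symmetric data and near-equal arms, the planned rule stays at 4.9–6.3% up to a ratio of 5.
- A reader might add the switching figure to the inflated error rates. They describe different situations. Switching in about half of trials was computed for normal data, where error is close to nominal; the inflation comes from skewed data.
- Mann–Whitney is valid for its own hypothesis. In the skewed scenarios the distributions really do differ. The fault lies in reading the p-value as evidence on means, and the SAP does not state that reading; its mean-and-SD reporting only invites it.
- A reader might infer that the whole Tsk analysis is unstable. The group-by-stage ANOVA is outside the switch, and about half of simulated trials never switch at any stage.
- The documents give no SDs or shapes, so they do not show that this trial's outcomes meet the harmful conditions. Stage-by-stage pretesting is the natural reading of Section 13, but is not stated.
- Welch gains little over Student here (6.8% against 6.7% in one lognormal run), because the arms are almost equal in size. The improvement comes from dropping the switch to ranks. The robust-SE model was not simulated.

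The exploratory label in Section 11 lowers the strength of any claim. It does not make a rank p-value and a mean with SD answer the same question.

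**Conclusion.** The point holds in a conditional form. The SAP leaves the tested quantity to a pretest, apparently for the primary endpoint as well, and reports means either way. This loss of a fixed target needs no distributional assumption.

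The error-rate consequence does need one. It is negligible for symmetric data. With skew and unequal spread together, a rejection read as a mean difference occurs in about 7–12% of trials for moderate skew and 14–29% for strong skew at spread ratios of 2–5, against at most about 8% for Welch. These figures rest on an assumed per-arm pretest at 0.05 and on assumed shapes, and cover between-group comparisons only. They do not show that any result of this trial is false. The change is worth making because it is cheap and uses only data already collected.

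**What to change.** Drop the pretest as a decision rule and keep normality checks as description. Name one method and one target per outcome:

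- **Tsk (including the primary minimum), log10 MDT and VDT:** mean difference with 95% CI, from Welch's t test or from a baseline-adjusted linear model with heteroscedasticity-robust standard errors. State which of the two.
- **TSS, CS and VAS at a given stage:** Mann–Whitney, reported as probability of superiority with 95% CI and not read as a mean difference.
- **Within-group comparisons:** likewise fix one paired method per outcome.

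Participants have been enrolled and, by Section 14, the data are deposited. The change should therefore be dated and disclosed under Section 17, with results under the planned rule shown alongside.

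The cost is SAP wording and a rerun. There are no new data, and the planned sample size does not change because it already rests on a t test. The downside is power for an untransformed, strongly skewed outcome with equal spread (about 72% against 86% in the case above), with little or no loss for near-normal outcomes. Log-transforming MDT may avoid most of that loss for MDT.

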1.4 Roles and responsibilities

Sponsor/Institution: Poznań University of Physical Education (Department of Physical Therapy and Sports Recovery).

Scientific lead: [[name]], PhD. Data management/statistics: [[name]], MSc. Thermal imaging lead: [[name]], MSc.

Corresponding author: [[name]], [[contact]].

2. Background and Rationale

Local cryotherapy with ice packs is widely used to alleviate pain and modulate cutaneous temperature and sensation. However, the short-term time-course of rewarming and contemporaneous changes in subjective thermal perception and somatosensory thresholds are not fully characterised in controlled, randomized settings. This study compares a 15-minute hand ice-pack application with a thermoneutral water-pack control, using infrared thermography (IRT) and a resistance thermometer (RT) alongside validated subjective scales and quantitative sensory testing (QST).

3. Objectives

Primary objective:

- To compare the effect of ice-pack vs thermoneutral pack on dorsal hand skin temperature (Tsk) during early rewarming after a 15-minute application.

Secondary objectives:

- To compare immediate post-cooling changes in mechanical detection threshold (MDT) and vibration detection threshold (VDT).
- To compare trajectories and peaks of subjective thermal sensation (TSS), thermal comfort (CS), and pain (VAS) during cooling and immediately post-cooling.
- To characterise agreement and systematic offset between ROI-averaged IRT and single-site RT across matched time points.

4. Trial Design

Randomized, parallel-group, two-arm laboratory experiment with a 1:1 allocation ratio (ice vs thermoneutral water). Single-centre. No blinding of participants; thermal image analysis performed offline by a rater not involved in data collection.

5. Study Setting

Single air-conditioned laboratory (Department of Physical Therapy and Sports Recovery, Poznań University of Physical Education). Ambient conditions monitored throughout (target $\sim 22.5 \pm 1.0$ °C, $55 \pm 7\%$ RH).

6. Participants

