8.2 Key secondary endpoints

- Dorsal hand Tsk at matched time points (I, IV–X) by IRT and RT; between-group differences and IRT–RT offsets.
- MDT change (post-cooling minus baseline; IV–I).
- VDT change (IV–I).
- Subjective scales: TSS (−4 very cold ... +4 very hot), CS (1 comfortable ... 5 extremely uncomfortable), VAS pain (0–100 mm). Outcomes include peak during cooling (II/III) and immediate post-cooling (IV).

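### For MDT and VDT, the only listed test of the IV–I change is within each arm; section 13 names no between-arm test of the change that the objective asks to compare

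*Combined protocol and SAP*

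**What the plan says.** Section 3 lists as a secondary objective "To compare immediate post-cooling changes in mechanical detection threshold (MDT) and vibration detection threshold (VDT"). Section 8.2 defines the matching endpoints as changes: "MDT change (post-cooling minus baseline; IV–I"), with VDT defined the same way. Section 9 schedules both thresholds at stages I and IV only.

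Section 13 then lists three kinds of test:

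- between-group comparisons at prespecified time points (Student's t or Mann–Whitney U);
- within-group pre–post comparisons, "paired Student’s t test (normal) or Wilcoxon signed-rank test (non-normal");
- a repeated-measures ANOVA with group × stage, restricted to skin temperature (Tsk).

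One significance rule covers all of them: alpha 0.05, "tests two-sided". Nothing in section 13 labels the within-group tests as descriptive.

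**The concern.** The trial is parallel and randomised, so an effect of ice is a difference between arms. For MDT and VDT, the between-group bullet compares levels at a time point and the group × stage analysis covers Tsk only. That leaves the within-group bullet as the only listed test of the IV–I change. It asks whether each arm changed, not whether the arms changed by different amounts.

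A change shared by both arms is plausible: both have repeat sensory testing, 15 minutes under a 400 g pack, and supine rest. With about 20 people per arm, a shared change can reach p < 0.05 in one arm and miss it in the other by chance. If that pattern were reported as an effect of ice, the control arm would no longer be doing its job for these two endpoints.

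**Working it through.** **Inputs.** From section 13: alpha 0.05, two-sided. From section 11: 20 ice and 19 control participants, no losses, and a design based on a "two-tailed independent-samples t-test" with d = 0.80 and power 0.80. The documents give no SD and no expected change for MDT or VDT, so the common change is an assumption and is varied below.

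**1. The plan's own figures.** The noncentrality for two independent means is d × √(n₁n₂/(n₁+n₂)).

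- 25 per group: 0.80 × √12.5 = 2.83, df 48, power 0.791.
- 26 per group: 0.80 × √13 = 2.88, df 50, power 0.807. The required 26 per group is reproduced.
- 20 and 19: 0.80 × √(380/39) = 2.50, df 37, power 0.682. The stated 0.68 is reproduced.

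The sample size therefore rests on a between-arm test.

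**2. Ice significant, control not, with no difference between arms.** Let δ be the true mean change divided by the SD of the change, the same in both arms. Power of the paired t test in an arm of size n comes from the noncentral t with noncentrality δ√n and df n − 1. The arms are independent, so

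P(ice only) = p_ice × (1 − p_control).

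For δ = 0.46 the noncentralities are 0.46 × √20 = 2.06 and 0.46 × √19 = 2.01, and the powers are 0.497 and 0.475. The product is 0.497 × 0.525 = 0.261.

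| Common change δ (SD) | p_ice | p_control | P(ice only) |
|---|---|---|---|
| 0 | 0.050 | 0.050 | 4.8% |
| 0.2 | 0.136 | 0.131 | 11.8% |
| 0.3 | 0.247 | 0.236 | 18.9% |
| 0.4 | 0.397 | 0.379 | 24.7% |
| 0.46 | 0.497 | 0.475 | 26.1% |
| 0.6 | 0.721 | 0.696 | 21.9% |
| 0.8 | 0.924 | 0.909 | 8.4% |
| 1.0 | 0.989 | 0.984 | 1.5% |

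The last column uses unrounded powers. The shape follows from p(1 − p), whose maximum is 0.25 at p = 0.5. The slight excess over 25% comes from the unequal arm sizes.

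**3. Direct test of change.** In 200,000 simulated trials per setting (normal changes, n = 20 and 19), a two-sample t test of the change scores rejected in 4.95% to 5.02% of trials at δ = 0, 0.3, 0.46 and 0.8. At δ = 0.46, simulation gave ice only in 26.0% of trials. In 23.7% of trials, ice only occurred together with a non-significant between-arm test, so the direct test would have contradicted most of those claims.

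**The case against.** The strongest reply is that this is an error of interpretation that the plan does not commit. No section says an effect of ice will be inferred from one significant arm. The bullet before the quoted one plans between-group tests, Tsk has a group × stage analysis, and the primary endpoint in section 8.1 is a between-group difference. All of that stands.

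MDT and VDT are not without a randomised comparison either. Stage IV is a scheduled time point for both, and section 12.2 says assignments stayed concealed until baseline assessments were complete. A between-group test at IV is therefore valid without subtracting baseline. That also stands, but it is a comparison of levels, while section 8.2 defines the endpoint as a change.

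The 26% can fairly be called a worst case. It needs a common change that gives each arm about 50% power, and the rate is much lower at either end of the table. Section 11 also declares the findings exploratory.

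Two stronger readings are tempting and not supported:

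- A reader might extend the argument to the within-group comparison of infrared thermography with the resistance thermometer. The section 3 objective there is device agreement and offset, for which pairing within participants is natural. No objective asks whether cooling alters the offset, and the rates above do not describe that analysis.
- A reader might infer that within-arm testing would hide a true difference whenever both arms change significantly. That would require ignoring the between-group tests that section 13 also plans.

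**Conclusion.** The point holds for MDT and VDT. Section 13 names no between-arm test of the endpoint defined in section 8.2, and the only listed test of that change is a within-arm one at the full 0.05 level, not marked descriptive. The primary endpoint, the Tsk analysis and the sample-size figures are unaffected.

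The size is conditional. If an effect of ice were claimed from significance in the ice arm alone, the false-claim rate per endpoint would run from about 5% with no common change, through at most about 26%, down to about 1.5% at 1.0 SD, against 5% for the direct test. This assumes normal change scores, paired t tests and the same standardised change in both arms. A reader might take one in four as the plan's error rate, but the documents do not support that: they neither give the size of a common change nor say that arm-wise p-values will be contrasted. Because this concerns key secondary endpoints and is cheap to correct, it should be changed.

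**What to change.** In section 13:

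1. Name the between-arm analysis for MDT and VDT: ANCOVA of the stage IV value on group with the stage I value as covariate, or a two-sample t or Mann–Whitney test of the IV–I change. Choose one as the main analysis.
2. Report within-arm changes as estimates with 95% confidence intervals, labelled descriptive.
3. State that every claim about an effect of ice rests on the between-arm contrast.

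The cost is SAP wording and one analysis per endpoint on data already collected; section 11 reports no losses among the 39 participants. The downside is that arm-wise p-values can no longer be quoted as evidence of an effect. The change should be recorded as an amendment with rationale and date, as section 17 provides. Section 11 already reports enrolment and follow-up as complete, so the entry should also say whether results had been seen when the change was made.

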8.3 Safety/harms

Monitoring for intolerance to cold (excess pain, numbness), skin irritation, or adverse events (e.g., frostbite risk). None anticipated under protocol; record and report any events.

9. Time Schedule of Enrolment, Interventions, and Assessments

Acclimatisation: 15 minutes (supine, hand supported on insulating mat).

Measurements at the following time points:

- I – end of acclimatisation (baseline)
- II – 7th minute of cooling
- III – 15th minute of cooling
- IV – immediately after removing the pack
- V – 5th minute of rewarming
- VI – 10th minute of rewarming
- VII – 15th minute of rewarming
- VIII – 20th minute of rewarming
- IX – 25th minute of rewarming
- X – 30th minute of rewarming

Schedule (✓ = administered):

- IRT (ROI mean Tsk): I, IV–X (eight images total)
- RT (single-site Tsk): continuous at 1-min; aligned to I–X for analysis
- TSS, CS, VAS: I, II, III, IV
- QST (MDT, VDT): I and IV

10. Data Collection Methods

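### The plan never uses stage-I skin temperature as a covariate, which costs precision; if stage I is a level of the Tsk ANOVA, the group main effect is also expected to be 7/8 of the post-pack effect.

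*Combined protocol and SAP*

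**What the plan says.** Section 13 (Statistical Analysis Plan) gives skin temperature a "two-way repeated-measures ANOVA for Tsk", with group × stage as the between-group form and Bonferroni-adjusted post hoc tests. It reports partial η² as the effect size. It names no covariate and does not list the levels of stage. Between-group comparisons at single time points use Student's t or Mann–Whitney tests, also unadjusted.

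Section 9 defines stage I as the baseline at the end of acclimatisation, before the pack goes on. Its schedule reads "IRT (ROI mean Tsk): I, IV–X (eight images total"), and section 8.2 lists as a key secondary endpoint "Dorsal hand Tsk at matched time points (I, IV–X") by IRT and RT, with between-group differences.

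The primary endpoint in section 8.1 is the minimum IRT Tsk over IV–X. Stage I is not part of it, and section 13 does not tie it to the ANOVA.

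Section 11 sizes the trial on a "two-tailed independent-samples t-test" and reports that "39 participants were enrolled and randomised", 20 to ice and 19 to control, against 52 required.

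**The concern.** Stage I is measured before treatment, and section 12.2 keeps the assignment concealed until baseline assessments are complete. The expected group difference at stage I is therefore zero. If stage I is one of the levels over which the group main effect is averaged, that effect and its partial η² describe a mixture of one untreated and seven treated readings.

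The larger matter is that people differ in hand temperature before any pack is applied. Without baseline adjustment, all of that variation stays in the error of the t tests and of the group main effect. Randomisation was simple, without blocking or stratification (section 12.1). With 20 and 19 participants the standard error of a chance baseline difference is √(1/20 + 1/19) = 0.32 SD, and the planned between-group tests do not correct for it. The baseline value exists for every participant, and the trial is short of its planned size.

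**Working it through.** **Inputs from the documents.** Two-sided α = 0.05 (section 13); "power = 0.80, anticipated effect size $d = 0.80" (section 11); 26 per group planned and 20/19 achieved (section 11); one pre-treatment and seven post-removal IRT stages (section 9).

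**Assumed, because the documents give no values.** Equal SDs across stages and arms; baseline-to-post correlation b; post-to-post correlation p, the same for every pair of post-pack stages. Effects are in SD units of one reading.

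**1. The plan's own figures.** With the noncentral t distribution at d = 0.80, power is 0.791 for 25 per group and 0.807 for 26, so 26 is the minimum. At 20/19 the noncentrality is 0.80 × √(20 × 19/39) = 2.50 on 37 df, and power is 0.682. Both stated figures (26 and about 0.68) reproduce.

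**2. Dilution of the main effect, if stage I is a level.** Expected group main effect = (0 + 7δ)/8 = 0.875δ, where δ is the mean post-pack effect. This needs no assumption about correlation.

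**3. Adjustment for a single post-pack outcome.** ANCOVA multiplies the error variance by 1 − b² and leaves 36 df. At d = 0.80 and 20/19:

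| b | 1 − b² | Power |
|---|---|---|
| no adjustment | 1 | 0.68 |
| 0.2 | 0.96 | 0.70 |
| 0.4 | 0.84 | 0.76 |
| 0.6 | 0.64 | 0.86 |
| 0.8 | 0.36 | 0.98 |

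**4. Averaged stages.** Variance of the seven-stage mean: V7 = (1 + 6p)/7. Variance of the eight-stage mean: V8 = (49·V7 + 1 + 14b)/64. Residual variance of the seven-stage mean after adjustment: VA = V7 − b². Relative efficiency of ANCOVA over the eight-level main effect = (1/VA)/(0.875²/V8).

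| p | b | V8 | VA | Relative efficiency |
|---|---|---|---|---|
| 0.8 | 0.2 | 0.694 | 0.789 | 1.15 |
| 0.8 | 0.4 | 0.738 | 0.669 | 1.44 |
| 0.4 | 0.4 | 0.475 | 0.326 | 1.9 |
| 0.6 | 0.6 | 0.650 | 0.297 | 2.9 |
| 0.8 | 0.8 | 0.825 | 0.189 | 5.7 |

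For a mean post-pack effect of 0.80 SD and p = b = 0.5, power is 0.81 for the eight-level main effect, 0.90 for the seven post-pack stages without adjustment, and 0.99 with adjustment. At that correlation, dropping stage I and then adjusting for it each add about 9 points.

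**5. The interaction.** In simulation (4,000 runs per scenario, p = b), a constant post-pack effect of 0.80 SD gives the group × stage test power of 0.47, 0.64 and 0.88 at correlation 0.3, 0.5 and 0.7. ANCOVA on the post-pack mean gives about 0.99 or more in each case. For an assumed effect falling from 1.6 to 0.3 SD over the seven stages, interaction power is about 0.98 or higher. Type I error was near 0.05 for every test (2,000 null runs).

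**The case against.** The strongest reply is that group × stage is the term section 13 writes out, and that term is not diluted. Stage I acts as its reference, and with a constant post-pack effect the interaction has power only because stage I is in the model. Undiluted contrasts are also planned at each time point, and the primary endpoint excludes stage I. All of this stands. A reader might infer that the trial's group effect in general, or its primary result, is diluted; the documents do not support that. What remains is that an omnibus interaction gives no adjusted group difference with a confidence interval, and that for a constant effect it is weaker than ANCOVA.

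It is also fair that the eight-level reading is an inference. Sections 8.2 and 9 give measurement and endpoint times, not model levels. If stage I is left out, the 7/8 point falls away and the missing covariate remains.

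A reader might take the 5.7-fold efficiency as the expected gain. It requires stage I to predict the post-pack readings as well as those readings predict one another. Stage I is separated from them by 15 minutes of ice in one arm, while IV–X lie about five minutes apart, so the low end of the range is plausible. The control pack is matched to limb temperature (section 7.2), so the baseline slope may also differ between arms.

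Finally, one might read the reported 0.68 as the power of the ANOVA. It belongs to the t test at d = 0.80. Section 11 already calls the findings exploratory.

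**Conclusion.** The point holds as one of efficiency and clarity, not validity. No planned analysis uses stage-I Tsk as a covariate, although all 39 participants have it. If stage I is a level of the ANOVA, which is the natural reading but is not stated, the group main effect is expected to be 12.5% smaller than the mean post-pack effect. Nothing else is diluted, and neither type I error nor the stated sample size is called into question.

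The gain from adjustment lies between slight and large. For a single outcome at d = 0.80 it is about 2 points of power at correlation 0.2 and 30 points at 0.8. For the averaged stages, relative efficiency runs from about 1.15 to 5.7 over the cases shown. These figures rest on equal SDs and on assumed correlations. For the primary endpoint the relevant correlation is between stage I and the minimum over IV–X, which the documents also do not give.

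**What to change.** In section 13, list the stage levels and model Tsk at IV–X with group, stage, group × stage, stage-I Tsk and baseline × stage, allowing for repeated readings on each participant. Fit it separately for IRT and RT, each with its own stage-I value, and report the adjusted group difference with a 95% CI. Analyse the primary minimum Tsk (IV–X, IRT) by ANCOVA on stage-I IRT Tsk. The IRT-versus-RT comparison within groups need not change.

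The cost is some SAP wording and a re-run on existing data. There is a small downside: enrolment is complete and section 14 describes the data as openly available. The change should therefore be documented under section 17 with date and rationale, labelled post hoc, and reported alongside the analysis as planned.

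### The plan sets out to characterise IRT–RT agreement, but its only IRT–RT analysis is a repeated-measures ANOVA, which addresses the mean offset and not the spread of individual differences

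*Combined protocol and SAP*

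**What the plan says.** Three places in the combined protocol and SAP bear on this.

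- **Section 3, secondary objectives:** "To characterise agreement and systematic offset between ROI-averaged IRT and single-site RT across matched time points". Two targets are named, agreement and offset.
- **Section 8.2, key secondary endpoints:** skin temperature by both methods at matched time points, with "between-group differences and IRT–RT offsets". Only the offset is carried forward.
- **Section 13, repeated measures:** a two-way repeated-measures ANOVA for skin temperature by group and stage, "and IRT vs RT within groups), with Bonferroni-adjusted post hoc tests". The effect size is partial eta squared.

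Section 9 schedules the paired readings: "IRT (ROI mean Tsk): I, IV–X (eight images total") for IRT, and one-minute RT readings "aligned to I–X for analysis". Section 11 reports that "In practice, 39 participants were enrolled and randomised", 20 to ice and 19 to control, and that "findings are interpreted as exploratory/hypothesis-generating".

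**The concern.** Agreement between two measurement methods has two parts: the mean difference, and the spread of individual differences around it. The planned ANOVA addresses the first part, including whether it changes during rewarming. Nothing in the plan commits to reporting the second.

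If the plan is followed as written, a reader will learn that one method reads higher on average by some amount, but not whether the two can differ by a little or a lot in a single hand. That second question is what agreement means in the objective. There is also a risk that the F test or partial eta squared is taken as a summary of agreement, because it is the only IRT–RT statistic planned. The documents do not say it will be read that way.

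**Working it through.** **1. Is the missing quantity planned elsewhere?** The documents give no figure for IRT–RT agreement, so there is none to reproduce. (The sample-size figures in Section 11 do reproduce: exact t-test power is 0.791 at 25 per group and 0.807 at 26, and 0.682 with 20 and 19. They concern the group comparison only.) The other candidate places are:

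- The paired tests in Section 13 compare pre with post, not one device with the other.
- The 10% re-analysis in Section 10.1 concerns the image rater.
- The descriptives line in Section 13 promises mean and SD but does not name paired differences.

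No section names limits of agreement, an SD of paired differences, or an intraclass or concordance correlation.

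**2. Would separate SDs for each device be enough?** No. If both devices have SD s and their readings correlate at r, the SD of the difference is s·√(2(1−r)). For assumed r of 0.5, 0.8 and 0.95 this is 1.00s, 0.63s and 0.32s. The same pair of device SDs fits a threefold range of spread.

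**3. Can F or partial eta squared stand in for agreement?** The documents give no SD for the IRT–RT difference, so I work in multiples of a fixed offset b. The ratio of SD to offset, the within-person correlation ρ of the differences, and a constant offset and SD across stages are assumptions.

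- Limits of agreement: b ± 1.96·SD.
- Noncentrality of the device effect over 8 stages: n·(b/SD)² / (ρ + (1−ρ)/8), with n − 1 error degrees of freedom.
- Partial eta squared, evaluated at F equal to the noncentrality: F/(F + n − 1).

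For n = 20 and ρ = 0.5 the denominator is 0.5 + 0.0625 = 0.5625, so at SD = b the noncentrality is 20/0.5625 = 35.6.

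| SD of difference | 95% limits | Noncentrality | Chance of significance | Partial eta squared |
|---|---|---|---|---|
| b | −0.96b to 2.96b | 35.6 | 100% | 0.65 |
| 2b | −2.92b to 4.92b | 8.9 | 81% | 0.32 |
| 4b | −6.84b to 8.84b | 2.2 | 29% | 0.10 |

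Over ρ from 0.3 to 0.8 the chances of significance are at least 99%, 65–93% and 22–40%. With n = 19 they are at least 99%, 62–91% and 21–38%.

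Down the table, agreement worsens while the evidence of a device difference weakens. Read up the table with the SD held fixed and the offset growing, agreement also worsens, yet rejection rises from 29% to 100%. At zero offset, rejection is 5% whatever the SD. Neither statistic tracks agreement.

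**4. How precise would the missing statistic be?** Per stage and arm, the 95% CI half-width is t/√n for the mean difference and t·√(1/n + 1.96²/(2(n−1))) for each limit, in units of the SD of the difference.

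- n = 20: 2.093/√20 = 0.47 SD, and 2.093·√(0.0500 + 0.1011) = 0.81 SD.
- n = 19: 2.101/√19 = 0.48 SD, and 2.101·√(0.0526 + 0.1067) = 0.84 SD.

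Pooling the 8 stages with a variance-components method, simulated under a common variance and ρ of 0.3 to 0.8, gives about 0.39 to 0.65 SD per limit at n = 20. Treating the 20 × 8 = 160 pairs as independent would give 0.27 SD, about 1.5 to 2.4 times too narrow.

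**The case against.** The strongest reply is that the spread is already covered. Section 8.2 makes the offset an endpoint and Section 13 promises mean and SD, so the offset at each stage might be reported with its SD, from which limits follow directly. That reading is possible but not stated. An offset may equally mean a difference of two means, and then no SD of paired differences appears.

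Second, the statistic is not lost. Section 14 says "De-identified IPD comprise participant-level values for prespecified outcomes and baseline characteristics", and Section 8.2 lists skin temperature by both methods, so anyone could compute it if both series are in the shared data. This stands, and it makes the gap one of analysis and not of data collection. Some spread can even be recovered from the planned output: the SD of person-averaged differences is |b|·√(n/F). But that equals only √(ρ + (1−ρ)/8) of the single-stage SD, which is 0.62 to 0.91 for ρ of 0.3 to 0.8, and ρ would not be reported.

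Third, the power figures describe a misreading that the plan does not propose, and they rest on assumed ratios and correlations. This also stands. They show only that F and partial eta squared are no substitute; they do not predict what this study will find. The eta squared values are nominal too: in the third row of the table the mean sample value is about 0.14, with a 5–95% range of roughly 0 to 0.38.

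Fourth, a region average and a contact site of about 15 mm² measure different things, so individual limits would mix spatial variation with device error. That is a caution for interpretation. The objective nevertheless asks for agreement between exactly these two measurements.

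**Conclusion.** The concern holds. The objective names agreement and offset, the endpoint keeps only the offset, and the planned analysis addresses only the mean offset and its course over stages. This is a mismatch between objective and method.

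The practical size in degrees Celsius is unknown, because the documents give no SD of the IRT–RT difference. The direction of the argument does not depend on that SD or on the assumed correlations: for a non-zero offset, F and partial eta squared fall as individual spread grows. The consequence is confined to one secondary objective in a study that calls its findings exploratory. The primary endpoint, the sample size and the group comparisons are unaffected. It should be fixed because the remedy is cheap and the objective is otherwise only half answered.

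**What to change.** Keep the ANOVA for the offset and add to Section 13:

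- for each arm at stages I and IV–X, the mean IRT–RT difference with its 95% CI, the SD of the paired differences, and the 95% limits of agreement with CIs;
- if stages are pooled, a repeated-measures limits-of-agreement method that accounts for the 8 pairs per participant;
- a statement that a non-significant F is not evidence of agreement.

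Record the change under Section 17 with its rationale, date and potential impact, and label it as added after data collection. If the team does not want this analysis, remove agreement from the objective in Section 3 and keep the offset.

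The cost is SAP wording and a short calculation on the scheduled pairs, 39 × 8 = 312. No new data, participants or image readings are needed. The drawback is that the per-stage limits will be imprecise, and the analysis remains exploratory.
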